9. RISKS TO SUBJECTS

The optimal treatment of patients undergoing ablation of AF remains an area of intense research. Patients undergoing ablation of AF experience a high rate of recurrent AF. There is evidence that dapagliflozin therapy may reduce the burden of AF. All patients enrolled in this study will have an FDA approved indication for dapagliflozin therapy. If a patient becomes pregnant during the course of the study, study drug should be discontinued immediately and CDC notified. The outcome of all pregnancies (spontaneous miscarriage, elective termination, ectopic pregnancy, normal birth or congenital abnormality) should be followed up and documented even if the patient was discontinued from the study medication.

The study is designed to prospectively evaluate whether dapagliflozin can reduce the burden of AF after ablation when compared to placebo.

Confidentiality Risk(s)

The risk to participating in this study may include a potential risk of a breach in confidentiality. Every effort will be made to keep the data confidential. To protect against this risk the information collected at each enrolling site will be entered by site personnel into a password protected electronic data capture (EDC) system. Subjects will be assigned a unique subject identification number at the time of registration, which is completed in the EDC system. The subject identification number is not connected with any PHI, such as date of birth or medical record.

Dapagliflozin Treatment Risks

Dapagliflozin has been studied in multiple clinical trials and has been found to be very well tolerated and has a high safety profile. However, the following serious risks have been associated with dapagliflozin treatment.

- 1. Volume Depletion: Dapagliflozin can cause intravascular volume depletion which may manifest as symptomatic hypotension or acute transient changes in creatinine. Acute kidney injury requiring hospitalization and dialysis has been reported in patients with type 2 diabetes receiving SGLT dapagliflozin. Patients with impaired renal function (eGFR less than 60 mL/min/1.73 m²), elderly patients, or patients on loop diuretics may be at increased risk for volume depletion or hypotension. Diuretic dosing may be titrated according to symptoms, signs, weight and other information per standard clinical practice. Temporary interruption of study drug may also be considered in subjects at potential risk of volume contraction.
- 2. **Ketoacidosis in Diabetes Mellitus** has been reported in patients with type 1 and type 2 diabetes receiving dapagliflozin. Some cases can be fatal. If ketoacidosis is suspected, the study drug will be discontinued. Patients on dapagliflozin may require monitoring and temporary discontinuation in situations known to predispose to ketoacidosis
- 3. Urosepsis and Pyelonephritis: SGLT2 inhibitors increase the risk for urinary tract infections (UTIs) and serious UTIs have been reported with dapagliflozin. Patients on study drug will be evaluated for signs and symptoms of UTIs and will be treated promptly.
- 4. **Hypoglycemia:** dapagliflozin can increase the risk of hypoglycemia when coadministered with insulin and insulin secretagogues. Patients with type 2 diabetes at randomization will continue to take their glucose-lowering therapies but dose adjustments

may be required at the discretion of the treating primary care physician as per standard of care glucose monitoring in diabetic patients. The dose of insulin and/or sulfonylurea therapy may be reduced to minimize the risk of hypoglycemia at the discretion of the primary treating physician per standard clinical practice.

- 5. Necrotizing Fasciitis of the Perineum (Fournier's Gangrene): Rare but serious, lifethreatening cases have been reported in patients with diabetes mellitus receiving SGLT2 inhibitors including dapagliflozin. Cases have been reported in females and males. Serious outcomes have included hospitalization, surgeries, and death. Patients will be assessed for pain or tenderness, erythema, swelling in the genital or perineal area, along with fever or malaise. If suspected, prompt treatment will be instituted and study drug will be discontinued.
- 6. **Genital Mycotic Infections:** dapagliflozin increases the risk of genital mycotic infections, particularly in patients with prior genital mycotic infections. Patients will be monitored and treat appropriately

The DAPA-HF trial enrolled 4,744 patients with heart failure with reduced ejection fraction (HFrEF) and randomized patients to treatment with dapagliflozin 10 mg once daily versus matching placebo. Dapagliflozin was stopped in 249 patients and placebo was stopped in 258 patients (10.5 vs 10.9%, P=0.71). Table below lists common adverse reactions associated with dapagliflozin therapy compiled from 12 placebo-controlled clinical trials. Standard of care monitoring of blood sugar values will be recommended for all diabetic patients enrolled in the study regardless of treatment allocation. Of note, treatment with an SGLT2 inhibitor was not shown to be associated with increased risk of hypoglycemia, and in the DAPA-HF study the rate of hypoglycemia was 1/2368 in the Dapagliflozin treatment arm vs. 4/2368 in the placebo arm. All adverse events during the trial will be prospectively collected and reviewed (detailed below in Table 2).

Adverse Reaction	% of Patients				
	Pool of 12 Placebo-Controlled Studies				
	Placebo N=1393	Dapagliflozin 5 mg N=1145	Dapagliflozin 10 mg N=1193		
Female genital mycotic infections*	1.5	8.4	6.9		
Nasopharyngitis	6.2	6.6	6.3		
Urinary tract infections ⁺	3.7	5.7	4.3		
Back pain	3.2	3.1	4.2		
Increased urination [‡]	1.7	2.9	3.8		
Male genital mycotic infections [§]	0.3	2.8	2.7		
Nausea	2.4	2.8	2.5		
Influenza	2.3	2.7	2.3		
Dyslipidemia	1.5	2.1	2.5		
Constipation	1.5	2.2	1.9		
Discomfort with urination	0.7	1.6	2.1		
Pain in extremity	1.4	2.0	1.7		

Table 2:	Adverse reactions in placebo-controlled studies of glycemic control
	reported in ≥2% of patients treated with dapagliflozin

Mitigation of risk associated with the Study Drug will follow drug labelling

recommendations per standard of care and procedures performed in the DAPA-HF clinical trial. These will include:

- 1. Glucose and HgBA1c monitoring in diabetic subjects will be performed as per standard of care. Patients with type 2 diabetes at randomization will continue to take their glucose-lowering therapies but these can be adjusted at the discretion of their diabetes health care provider. The dose of insulin and/or sulfonylurea therapy may be reduced to minimize the risk of hypoglycemia at the discretion of the primary treating physician per standard clinical practice.
- 2. Study drug will permanently be discontinued if pregnancy or diabetic ketoacidosis occur. Dose reduction (to dapagliflozin 5 mg daily or matching placebo) or temporary discontinuation may be considered in cases of acute, unexpected declines eGFR (while investigating other causes such as nephrotoxic drugs, urinary traction infection, or obstruction. Similarly, in cases of volume depletion and/or hypotension, alternative causes should be considered (e.g. gastrointestinal fluid loss, use of non-essential blood pressure-lowering drugs) and the dose of concomitant diuretic therapy re-assessed and reduced, if appropriate. Temporary interruption of study drug may also be considered, prophylactically, in subjects at potential risk of volume contraction/hypotension, such as subjects with an acute medical illness potentially causing volume depletion because of inadequate fluid intake or fluid/blood losses (e.g. gastroenteritis, gastrointestinal hemorrhage), or subjects undergoing major surgery.
- 3. Subject notification of possible adverse events at enrollment.
- 4. Adverse event data collection and independent DSMB monitoring.

Placebo Arm Treatment Risks

Subjects randomized to the placebo arm will undergo standard of care management following AF ablation. With regard to AF outcomes there are no known risks associated with not treating with dapagliflozin in the placebo arm.

10. POTENTIAL BENEFITS TO SUBJECTS

Subjects randomized to dapagliflozin may experience a lower burden of AF following ablation.

11. COSTS FOR PARTICIPATION

There are no additional costs to the subject. All office visit/procedures will follow standard of care guidelines and are covered by subject's medical insurance. The randomization process will not add to subject costs.

12. PAYMENT FOR PARTICIPATION

There will be no compensation for participation in this study.

13. SUBJECT WITHDRAWALS

Randomized subjects may be withdrawn prior to the study completion for a variety of reasons including:

- a) Subject withdraws consent for any reason and will not be replaced.
- b) Subject is lost to follow up despite best efforts to locate the subject and will not be replaced.
- c) Subject withdrawn by physician.

Subjects may be considered lost to follow up after missing two consecutive follow-up visits with documented efforts to contact the subject.

These subjects will not undergo any additional study activities after withdrawal. Data collection will occur until the date of withdrawal and utilized in the study analysis. Withdrawn subjects who have been randomized will not be replaced. Withdrawn subjects will be requested to return all study drug at the time of withdrawal if contact is made with the subject. Subjects will not be required to withdraw from the study if the study drug is discontinued or unblinded. Subjects will not be required to be withdrawn from study if the subject decides not to take the study drug.

14. PRIVACY AND CONFIDENTIALITY OF SUBJECTS AND RESEARCH DATA

Data collected during this study will be obtained for research purposes and derived from study procedures, CIED interrogation data, subject records and subject visits. All study data will be stored in perpetuity in a password-protected database located at the CCRC per Section 15 and de-identified. Data will be accessible to the research sites and people who work with the University of Rochester which may use the results of the study for other research purposes. To protect confidentiality and privacy, subject data will be assigned a code using a unique subject ID number at the time of randomization and linked to subject identifiers that are stored separately in a study log solely maintained by the enrolling site study coordinator. The electronic data will be directly entered and extracted from computer system for data collection using encryption and physical controls. There is no plan to share, transmit or transfer the data. The subject's email address will not be stored nor transmitted with the study data if the subject opts for electronic consent signature via the study website.

15. DATA / SAMPLE STORAGE FOR FUTURE USE

Study coordination, database management and statistical analysis will be performed by the Clinical Cardiovascular Research Center (CCRC) at the University of Rochester Medical Center (U of R) acting as the Coordination and Data Center for the study.

Data will be captured using TrialMaster, a HIPAA compliant secure web-based electronic data capture (EDC) system that is used to support the clinical research process. Data that are entered are validated against a set of rules to ensure the accuracy of the clinical data. The TrialMaster system is housed on CCRC servers that are housed behind the U of R firewall in the U of R Primary Data Center, where physical access and environmental controls are in place to protect the data. All access to the data is through an authentication process provided by the system and over the encrypted, secured U of R network, which both provide the necessary controls to prohibit unauthorized access to the clinical data. Continuous availability of the data is provided by mirroring the databases to servers located in a physically separate Secondary Data Center. Additional details are in the Data Safety Monitoring section below. Only authorized research personnel working on the project will have access to the data.

Only enrolling site personnel authorized by the site Principal Investigator will have access to the EDC system. Study personnel at each site delegated with EDC permission will be required to complete EDC training before receiving access to the system. Site personnel with EDC permission will have access to the system 24/7 for data entry. Study personnel will initially enter

all data related to the randomization and baseline data collection and will then complete data entry after each identified data collection timeframe per Table 1.

Data collected may be used for the development of future research studies. We will maintain the confidentiality of the data throughout the process. The subject will be given the option to agree or decline to be re-contacted in the future by the study doctor, or someone from the study team, about using the subject's information for research that is not described in the DAPA-AF study consent form; or to participate in other research. Re-contacting the subject may be made in person, by phone or by mail.

16. DATA AND SAFETY MONITORING PLAN

Adverse Event (AE) Data

An AE is the development of an undesirable medical condition or the deterioration of a preexisting medical condition following or during exposure to study drug, whether or not considered causally related to the product. An undesirable medical condition can be symptoms (e.g. nausea, chest pain), signs (e.g. tachycardia, enlarged liver) or the abnormal results of an investigation (e.g. laboratory findings, electrocardiogram). In clinical studies, an AE can include an undesirable medical condition occurring at any time, including run-in or washout periods, even if no study drug has been administered. The term AE is used to include both serious and non-serious AEs.

All adverse events will be collected after subject randomization at all subject contacts as indicated in Table 1. Adverse event data will be captured in the electronic data capture system and enrolling site investigators are responsible for reporting to and following reviewing Institutional Review Board (IRB) guidelines and reported to the DSMB. De-identified adverse event safety data will be provided to Astra-Zeneca, the study drug manufacturer as reported in a password-protected file per post-market FDA regulations.

Adverse Event Reporting

Enrolling site investigators shall report in the CDC electronic data collection system within five business days of PI awareness non-serious adverse events that are only related or suspected to be related to study activities and/or study medication, and all serious adverse events regardless of the relationship to the study activities and/or study medication per the serious event definitions below. Events leading to death or death (if event leading to death) of a subject must be reported as an adverse event, per the serious adverse event definition below. The enrolling site PI is aware that investigators are responsible for reporting to and following the guidance of any other applicable oversight bodies, including the reviewing Institutional Review Broad (IRB).

The CDC will be forwarding relevant documents to the Chair of DSMB for review and the Chair will determine whether individual case will require immediate assessment by the full DSMB committee or it could be assessed during electively scheduled DSMB meeting. Any SAEs meeting criteria for expedited reporting, the PI will be responsible for reporting to FDA and will notify AZ concurrently. We will also inform Astra Zeneca, the study drug manufacturer, about reported adverse events per FDA post-marketing regulation requirements.

Serious Adverse Event Definition

This population is at increased risk of heart failure, death, and poor clinical outcomes. A serious adverse event (SAE) is defined as any adverse medical experience that results in any of the following outcomes regardless of causal relationship with the study drug: Results in death

• Is immediately life-threatening or results in death

- Requires in-patient hospitalization or prolongation of existing hospitalization
- Results in persistent or significant disability/incapacity or substantial disruption of the
- ability to conduct normal life functions
- Is a congenital abnormality or birth defect
- Is an important medical event that may jeopardize the subject or may require medical
- Intervention to prevent one of the outcomes listed above.

Unanticipated Problem Definition

An Unanticipated problem is any event, experience, issue, instance, problem or outcome that meets all 3 of the following criteria:

- Is unexpected in terms of the nature, severity or frequency given the research procedures that are described in the protocol-related documents AND in the characteristics of the population under study or if cause is study drug an adverse event or suspected adverse reaction is considered unanticipated if it is not listed in the study drug package insert or is not listed at the specificity or severity that has been observed per the study drug package insert.
- Is related or possibly related to participation in research. This means that there is a reasonable possibility that the incident may have been caused by the procedures and/or study drug involved in the research study.
- The incident suggests that the research places the subject or others at greater risk of harm (physical, psychological, economic or social) than was previously known or recognized OR results in actual harm of the subject or others. An unanticipated problem generally required a change in policy or procedure, warrants consideration of substantive changes to the protocol/consent or other immediate corrective actions in order to reduce the risk or eliminate immediate hazard.

Data and Safety Monitoring Board

A data and safety monitoring board (DSMB) will be appointed to independently monitor the conduct and the outcome of the trial. The DSMB will be responsible for monitoring the safety and well-being of the subjects participating in this study and ensuring the ethical conduct of the trial. The DSMB will be responsible for safeguarding the interests of study participants, assessing the safety and efficacy of study procedures and study drug, and for monitoring the overall conduct of the study.

The main focus of DSMB activity will be to monitor complications after randomization. For all randomized subjects, data on clinical events including adverse events, cardiovascular hospitalizations, and death will be collected and provided to the DSMB for evaluation of risks associated with participation in the trial.

The DSMB will be an independent group advisory to the Coordination and Data Center study principal investigator and asked to provide recommendations about starting, continuing, and

stopping the study. In addition, the DSMB asked to make recommendations, as appropriate, about:

- Efficacy of the study intervention
- Benefit/risk ratio of procedures and participant burden
- Selection, recruitment, and retention of participants
- Adherence to protocol requirements
- Completeness, quality, and analysis of measurements
- Amendments to the study protocol and consent forms
- Performance of individual sites
- Participant safety

The board will be comprised of 4 independent members: (1) 1 statistician with experience in clinical trials; (2) 1 cardiologist with expertise in clinical trials; (3) 1 electrophysiologist with expertise in ablation and arrhythmia treatment; and (4) 1 endocrinologist with expertise in diabetic monitoring and treatment. The DSMB will meet before trial commencement, after 25 subjects are enrolled and when the 6 month follow-up visit is completed on the last randomized subject. It is anticipated that these meetings will take place via conference call. One of the clinicians will be selected to chair the committee and will serve as the principal representative of the group. The Chair of the committee will be informed monthly about adverse events and will monitor safety of the subjects during interim time between formal meetings of DSMB.

Reports will be sent by the CDC to the DSMB chair, to report data on expected and unexpected adverse events as they are reported by the enrolling site. The Chair of the DSMB will have the right to convene additional meetings with all DSMB members when needed. The DSMB will carefully consider if these events are consistent with anticipated clinical outcome, i.e. unrelated, or a consequence of the study activity and/or study drug, i.e. related. Information on all these events will be sent to DSMB Chair as they occur and in addition, a full DSMB report including an adverse event summary will be prepared before every elective DSMB meeting.

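### Serious adverse events, including deaths, have the same five-business-day site reporting limit as related non-serious events, so central safety review can start on information a week old

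*Combined protocol and SAP*

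**What the plan says.** Under Adverse Event Reporting, Section 16 fixes the site's deadline in a single sentence. It begins "Enrolling site investigators shall report in the CDC electronic data collection system within five business days of PI awareness non-serious adverse events", narrows these to events related or suspected to be related to the study, and continues "and all serious adverse events regardless of the relationship to the study activities and/or study medication per the serious event definitions below". On fatal events it adds: "Events leading to death or death (if event leading to death) of a subject must be reported as an adverse event". That brings deaths under the serious-event definition and attaches no separate time.

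Two later steps are described without a time limit. One is the expedited route: "Any SAEs meeting criteria for expedited reporting, the PI will be responsible for reporting to FDA and will notify AZ concurrently". The other is the step to the board: "The CDC will be forwarding relevant documents to the Chair of DSMB for review", after which the chair decides whether a case goes to the full board at once or waits for a scheduled meeting.

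Under Data and Safety Monitoring Board, the same section says "The Chair of the committee will be informed monthly about adverse events". It also says that reports go to the chair as sites file them, and "Information on all these events will be sent to DSMB Chair as they occur". The board is to meet before the trial starts, after 25 subjects are enrolled, and when the last randomized subject has completed the 6-month visit.

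**The concern.** The plan gives a death or a life-threatening event no more urgency at the site-to-centre step than a minor related complaint. Yet it expects the chair to judge which individual cases cannot wait. That judgement is only as timely as the report that feeds it.

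Case-by-case review matters more here than in many trials because the board meets so rarely. Section 9 lists rare but potentially fatal risks of the study drug, including ketoacidosis and necrotizing fasciitis of the perineum. With 12 or 13 subjects per arm, one serious event is about 8% of an arm (1/13 = 7.7%, 1/12 = 8.3%), so a single case can carry weight in a judgement of risk.

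**Working it through.** The plan gives no calendar-day figure to reproduce, and no power or sample-size formula is involved. The check is a date conversion followed by a reading of the reporting chain.

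**Inputs**
- Limit: five business days, counted from PI awareness (Section 16, Adverse Event Reporting).
- Events covered: related non-serious events and all serious events (same sentence).
- Time limits for expedited reporting, for forwarding to the chair and for IRB reporting: none stated (Section 16).
- Planned size: 25 subjects (Sections 4.1 and 17). Enrollment period: 18 months (Section 4.1).
- Public holidays within the window: my assumption, none, one or two.

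**Step 1. Business days to calendar days.** Day 0 is the day of awareness. Without a holiday, calendar days = 5 + weekend days crossed after day 0.
- Monday to Friday: 5 + 2 = 7.
- Saturday: 5 + 1 = 6.
- Sunday: 5 + 0 = 5.

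A holiday moves the deadline to the next working day, which can add a weekend. For example, with awareness on a Friday, one holiday moves the deadline from the following Friday to the Monday after it: 7 + 3 = 10. The longest windows are:

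| Day of awareness | No holiday | One holiday | Two holidays |
|---|---|---|---|
| Monday to Wednesday | 7 | 8 | 9 |
| Thursday | 7 | 8 | 11 |
| Friday | 7 | 10 | 11 |
| Saturday | 6 | 9 | 10 |
| Sunday | 5 | 8 | 9 |

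**Step 2. The chain from event to chair.**
1. Event to PI awareness: no bound stated. Scheduled contacts are at 3, 6, 9 and 12 months, each ± 1 month.
2. PI awareness to database entry: up to five business days, so normally up to 7 calendar days.
3. Coordinating centre to chair: no bound stated, though the wording points to forwarding as reports arrive.
4. Chair's decision on whether the whole board must look at once.

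Only link 2 has a number, and that number is the same whether or not the event is serious.

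**Step 3. Is there a faster stated route?** Section 16 also makes investigators responsible for reporting under IRB guidance, and Section 3 makes the coordinating centre the liaison with the reviewing IRB for unaffiliated sites. The expedited route to the regulator, with notice to the manufacturer, is a further path. Either might bring earlier notice, but the documents attach no time to either, so neither guarantees central knowledge before the limit in link 2.

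**Step 4. What the board calendar covers.** The first meeting after the trial starts is tied to 25 enrolled subjects, which is the whole planned sample. It therefore falls near the end of an 18-month enrollment period. Section 4 equates enrollment with consent, so screen failures could bring this meeting somewhat ahead of the last randomization. Until then, the chair's review of single cases, and any extra meeting the chair calls, is the board's safety function.

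**The case against.** The strongest reply is that five business days is a ceiling, that sites may report sooner, and that IRB or regulatory rules may require it. The documents contain no serious-event standard that the limit breaches, so the choice of a shorter clock is a matter of design. All of that is correct. It does not supply a faster limit in this plan.

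Three stronger readings are tempting and should not be adopted.

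- A reader might infer that the chair is told only monthly, and so up to about 5 weeks late (7 + about 30 = about 37 days). This needs the monthly sentence to override two others in the same section and the single-case route under Adverse Event Reporting. The sentences read more naturally as layers: single-event notices, a monthly update, and a full report before each meeting. What remains is a small ambiguity, since the text does not say which notice covers which events.
- A reader might infer that the chair-notice wording itself lets a fatal event go unseen centrally. It cannot: notice to the chair comes after central receipt. Only the site deadline bears on that.
- A reader might infer that a week's delay takes away protection against the listed fatal risks. Section 9 leaves subject-level action with the site: study drug is discontinued when ketoacidosis is suspected, and suspected perineal fasciitis is treated promptly with discontinuation. Neither waits for the board.

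Nor do the documents show that database entry is the only way the centre can learn of an event, since the IRB and expedited routes exist.

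**Conclusion.** The concern holds in limited form. Serious events, deaths included, share one limit with related non-serious events: normally up to 7 calendar days from PI awareness, 5 or 6 if awareness falls on a weekend, and at most 8 to 10 with one holiday or 9 to 11 with two, depending on the weekday. Time from event to awareness comes on top and is not bounded. No faster site-to-centre limit is stated anywhere, so the chair's urgent-case decision can start on week-old information.

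The consequence is slower central oversight; the subject's own care is not held up. The conclusion rests on reading the limit as a maximum and on the absence of any stated time for the other routes. The holiday figures are assumptions. The present rule is explicit and internally workable, so this is a worthwhile, inexpensive improvement, not a defect that undermines the trial.

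**What to change.** In Section 16, Adverse Event Reporting, split the sentence. Give serious adverse events their own shorter clock, for example initial database entry within 24 hours of site awareness, with follow-up detail within five business days. The 24 hours is my proposal; the documents contain no such figure, and the point does not depend on that exact value. Keep five business days for related non-serious events.

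As a minor clarification under Data and Safety Monitoring Board, state that notices of serious events go to the chair on receipt and that the monthly report is a cumulative listing.

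The cost is protocol wording and a memo to the seven sites. Site workload rises slightly, but about 25 subjects should produce few serious events, and Section 15 already gives site staff access to the data system at all hours.
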